### Study summary

This will be a randomised, double-masked, contralateral, cross-over study in which 28 subjects will wear the Avaira Vitality contact lens (fanfilcon A) and the Biofinity lens (comfilcon A), each lens having been soaked overnight in a lens care product (“solution”), Lite or Hy-Care. Follow-up visits will take place after approximately 2 hours of lens wear; with a two-day ‘wash-out’ period between the solutions. Key outcome measures for this study are a range of short term biomicroscopy signs. A study summary is shown in Table 1.

Visit	Procedures
1	Informed consent Explanation of study procedures and subject instructions Ocular and contact lens history Medical history [Redacted] Biomicroscopy [Redacted] Subjective scores
1b	Subjective scores [Redacted]
2	Biomicroscopy Biomicroscopy [Redacted] Subjective scores
2b	Subjective scores [Redacted] Biomicroscopy Exit form signed and payment issued

Table 1: Study summary.

## Section 1. Overview

### 1.1 Background

Various reports in the literature have reported significant levels of corneal staining with certain combinations of contact lens types and care systems. This phenomenon has been attributed to the binding of polyhexamethylene biguanide to lipids on the surface of a contact lens, and the subsequent release of the preservative at the ocular surface; although this theory has not been convincingly proven. The precise significance of such corneal staining is not generally agreed. This project seeks to examine the biomicroscopic response and other shortterm clinical responses after approximately two hours exposure to a range of contact lenses and solution combinations.

### 1.3 Study objectives

The objective of this study is to compare the short-term clinical response to all combinations of two lens types: Avaira Vitality and Biofinity with two care systems: Hy-Care and Lite.

The primary variables of interest are short-term biomicroscopy signs. Other variables of interest include subjective response [REDACTED].

### 1.4 Study design

This clinical study will be a randomised, double-masked, contralateral study, controlled by cross-comparison where the short term clinical response to each lens/care system combination will be assessed at a single study site. 28 subjects will wear lenses for approximately 2 hours on two days.

### 1.5 Statistical considerations

The principal hypothesis to be tested in this work is that biomicroscopy scores will not be different between the lens/solution combinations evaluated.

[REDACTED], biomicroscopy [REDACTED] and subjective responses will generate data that are likely to be continuous and normally distributed. As such, these will be compared using linear regression models or other parametric methods.

[REDACTED]

[REDACTED] Deviations from this statistical plan will be discussed in the final report. Deviations may be necessary due to differences between the actual data distribution compared with the anticipated data distribution.

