#### **1.5.1 Power analysis**

The principal outcome variable to be tested in this work is corneal staining. If 22 subjects complete the work, the power of the study to detect a difference of 5 units for 'extent of corneal staining' on a 0-100 scale for corneal staining (assuming an alpha of 0.05, a two-tailed paired analysis and a standard deviation of intra-subject differences of 8 units) is 0.80. To cater for any subject discontinuations, 28 subjects will be recruited for the work.

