#### 2.1.4 Exclusion criteria

Subjects will not be eligible to take part in the study if:

1. They have an ocular disorder which would normally contra-indicate contact lens wear.
2. They have a systemic disorder which would normally contra-indicate contact lens wear.
3. They currently wear reusable soft contact lenses in both eyes.
4. They are using any topical medication such as eye drops or ointment.
5. They have had cataract surgery.
6. They have had corneal refractive surgery.
7. They have any corneal distortion resulting from previous hard or rigid lens wear or have keratoconus.
8. They are pregnant or breast-feeding.
9. They have any ocular abnormality which would, in the opinion of the investigator, normally contraindicate contact lens wear.
10. They have Type 2 or greater corneal staining prior to lens application at Visit 1 or 2 [REDACTED]
11. They have corneal staining covering greater than 20% in any corneal region at Visit 1a or 2a [REDACTED]
12. They have any infectious disease which would, in the opinion of the investigator, contraindicate contact lens wear or pose a risk to study personnel; or they have any immunosuppressive disease (e.g. HIV), or a history of anaphylaxis or severe allergic reaction.
13. They have taken part in any other contact lens or care solution clinical trial or research, within two weeks prior to starting this study.

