### 2.6.3 Randomization of lenses and care regimens

This is a double-masked (participant, investigator), contralateral, crossover study design. Lenses are worn as an unmatched pair. In order for subjects to use each possible combination of lens/solution, two dispensing visits will be required. The order of lens/solution use is detailed in the randomization schedule (██████████). The randomization will be such that across the two study days, each eye will wear both of the study lenses. That is, if for the first solution the randomization determines that the right lens will wear the Avira Vitality lens and the left eye will wear the Biofinity lens, the laterality of the lenses will be swapped for the second solution.

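### Optional improvement: when comparing post-wear staining, adjust for the pre-lens staining grade already collected that day, using a model that respects the two-eye, two-day structure

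*Combined protocol and SAP*

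**What the plan says.** - **Hypothesis and method (1.5).** "The principal hypothesis to be tested in this work is that biomicroscopy scores will not be different between the lens/solution combinations evaluated". On method: "As such, these will be compared using linear regression models or other parametric methods". The visible text names no covariate and no subject, eye or day term. Redacted blocks follow that sentence.
- **Outcome and power (1.5.1).** Corneal staining is the principal outcome. With 22 completers, a 5-unit difference in extent (0-100 scale) and alpha 0.05, power is given as 0.80, assuming "a two-tailed paired analysis and a standard deviation of intra-subject differences of 8 units".
- **Timing of the response.** The Study summary says "Follow-up visits will take place after approximately 2 hours of lens wear", and 1.1 aims to "examine the biomicroscopic response and other shortterm clinical responses after approximately two hours exposure". The natural reading is a comparison of extent after wear, at Visits 1b and 2b.
- **Pre-lens grade (3.2.2, 3.2.4).** Staining is graded in five regions before lenses are fitted at Visit 1 and again at Visit 2. Grading of each eye is explicit for Visit 2; the matching Visit 1 text is partly redacted.
- **Its visible use (2.1.4, 3.2.4).** Eligibility ("They have Type 2 or greater corneal staining prior to lens application at Visit 1 or 2"; "They have corneal staining covering greater than 20% in any corneal region at Visit 1a or 2a") and the optional repeat of Visit 2.
- **Design (2.6.3).** "In order for subjects to use each possible combination of lens/solution, two dispensing visits will be required". Lens laterality is swapped for the second solution, so each subject gives four eye-visits (two eyes, two days).

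**The concern.** A staining grade taken just before exposure can carry information about the grade two hours later. Pairing within subject removes stable differences between subjects. It does not remove variation in how a particular eye starts on a particular day. A same-eye, same-day covariate can remove some of that at no cost in data, because the measurement is already scheduled and regression is already named.

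What is at stake is precision on the principal outcome. At 22 completers the plan has no margin over 80% power, so a useful covariate would give some and an uninformative one would take a little away. How the covariate enters also matters, because the four eye-visits of one subject are not related to each other in the same way.

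**Working it through.** **1. The plan's own figure.** Inputs from 1.5.1: n = 22, difference 5, SD of paired differences 8, two-sided alpha 0.05.

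- Noncentrality = 5 / (8/√22) = 2.93, df = 21, critical t = 2.08.
- Power from the noncentral t = **0.798**, which agrees with the stated 0.80.
- Expected 95% CI half-width ≈ 2.08 × 8/√22 = 3.55 units.

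**2. The same contrast with the covariate.** Regress the post-wear paired difference on the pre-lens paired difference; the intercept estimates the treatment difference. Let r be the within-subject correlation of those two differences. The documents do not give r, so a range is assumed.

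- Residual SD = 8√(1 − r²), df = n − 2 = 20.
- Variance inflation for the estimated slope, on average = 1 + 1/(n − 3) = 1 + 1/19.
- Noncentrality = 5 / [8√(1 − r²) × √((1 + 1/19)/22)].

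| r | Residual SD | Noncentrality | Power, n = 22 | Completers for 80% |
|---|---|---|---|---|
| unadjusted | 8.00 | 2.93 | 0.798 | 23 |
| 0 | 8.00 | 2.86 | 0.776 | 24 |
| 0.2 | 7.84 | 2.92 | 0.792 | 23 |
| 0.3 | 7.63 | 3.00 | 0.813 | 22 |
| 0.5 | 6.93 | 3.30 | 0.880 | 19 |

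Adjusted and unadjusted power are equal at r of about 0.23. Simulation of the adjusted contrast (20,000 runs per value) gave 0.775, 0.812 and 0.878 at r = 0, 0.3 and 0.5, with type I error of 0.048 to 0.052.

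**3. Why the model form matters.** Suppose all four eye-visits go into one regression with subject and combination terms and a single residual variance. As an illustration, assume subject-by-day variance 15 and residual variance 22.

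- Same-day difference (two eyes): variance 2 × 22 = 44.
- Cross-day difference: variance 2 × (15 + 22) = 74.
- Each subject has 2 same-day and 4 cross-day pairs, so the average is (2 × 44 + 4 × 74)/6 = 64 = 8², matching the planned SD.
- The regression applies 64 to every contrast. With 88 − 22 − 3 = 63 df, critical t = 2.00.
- Same-day type I error ≈ 2 × P(Z > 2.00 × 8/√44) = 2 × P(Z > 2.41) = 0.016.
- Cross-day type I error ≈ 2 × P(Z > 2.00 × 8/√74) = 2 × P(Z > 1.86) = 0.063.

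Simulations under these assumptions gave about 0.01 to 0.02 for same-day contrasts and 0.06 to 0.08 for cross-day contrasts. Per-subject paired contrasts, adjusted or not, stayed near 0.05 (0.03 to 0.06 over 1,000 runs). The swap in 2.6.3 makes unequal correlation plausible: comparing the lenses under one solution is same-day, between eyes; comparing the solutions for one lens differs in both day and eye.

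**4. Wash-out.** The Visit 2 pre-lens grade follows the first exposure. If, for example, 10% of a 5-unit effect remained in that grade but not in the post-wear score, a slope of 0.3 would shift the Visit 2 comparison by 0.10 × 5 × 0.3 = 0.15 units.

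**The case against.** - **Redaction.** Model terms could sit in the redacted parts of 1.5, and linear regression already allows a covariate. This stands. A reader might infer that the plan omits baseline adjustment; the documents show only that the visible text does not state it.
- **The gain may not exist.** This also stands. The limits in 2.1.4 narrow the pre-lens range, subjects attend without having worn lenses that day, and r is what remains after stable subject differences are removed. At r of 0.2 or less the paired contrast loses slightly. A reader might take the 0.880 at r = 0.5 as the expected benefit; nothing in the documents supports that value.
- **One pooled regression looks more powerful.** With equal correlations between all four eye-visits it would have power of 0.823 unadjusted, and 0.817, 0.851 and 0.911 adjusted at r = 0, 0.3 and 0.5. A reader might set 0.851 or 0.911 against the plan's 0.80. That is not a fair comparison: the step from 0.798 to 0.823 comes from pooling degrees of freedom, not from the covariate. All these figures need an equal-correlation assumption that the documents do not establish and that the design makes doubtful.
- **The covariate at Visit 2 is measured after treatment.** True. The shift in the example is small, but its 10% residue is arbitrary. This is a reason to show the unadjusted result, not a reason against adjusting.

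**Conclusion.** An optional, inexpensive improvement. Nothing in the plan is wrong on this point: the unadjusted paired comparison is valid, and the stated power is right for its inputs. A reader might infer that the comparison is invalid or underpowered without the covariate; the reproduced figure rules that out.

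For the contrast that 1.5.1 powers, the effect on power runs from a loss of about 2 points (0.798 to 0.776) if the pre-lens grade is uninformative to a gain of about 8 points (to 0.880) at r = 0.5. This rests on the planned SD of 8 applying to post-wear differences, on an assumed range for r, on both eyes being graded before fitting at Visit 1 as at Visit 2, and on a wash-out that leaves the Visit 2 pre-lens grade largely free of the first exposure. Confidence is medium, because r is unknown and part of 1.5 cannot be read.

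**What to change.** Unless the redacted text of 1.5 already does so, add to 1.5:

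- The response is post-wear staining extent (Visits 1b and 2b), compared between lens/solution combinations with the same-eye, same-day pre-lens extent (Visits 1 and 2) as a covariate.
- The model is one of two, named in advance: per-subject paired contrasts (post-wear difference regressed on pre-lens difference), or a mixed model over the four eye-visits with combination, day and eye terms and subject, subject-by-day and subject-by-eye (or unstructured) covariance. A regression with one common residual variance is not used.
- The five regional grades are combined by the same rule before and after wear.
- If a visit was repeated, the pre-lens value comes from the day the lenses were worn.
- The adjusted difference is reported with its 95% CI, and the unadjusted paired result alongside.

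**Cost:** a few sentences, with no new data, visits or subjects. The statistical price is about 2 points of power in the paired contrast if r is near 0, and reliance on the wash-out for the Visit 2 grade.

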#### **1.5.1 Power analysis**

The principal outcome variable to be tested in this work is corneal staining. If 22 subjects complete the work, the power of the study to detect a difference of 5 units for 'extent of corneal staining' on a 0-100 scale for corneal staining (assuming an alpha of 0.05, a two-tailed paired analysis and a standard deviation of intra-subject differences of 8 units) is 0.80. To cater for any subject discontinuations, 28 subjects will be recruited for the work.

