**3.2.3 Visit 1b (follow-up)**

The following procedures will be performed:

- 1. The subject will be asked to score the following reactions:

- Comfort before removal
- Dryness

[REDACTED]

[REDACTED]

[REDACTED]

- Overall score

[REDACTED]

[REDACTED]

5. The lenses will be removed and discarded.

[REDACTED]

7. A complete biomicroscopic examination will be conducted as outlined in Visit 1.
8. The subject will then be discharged and asked to return for Visit 2. Subjects are reminded to attend wearing spectacles, and not to wear habitual contact lenses on the day of the visit.

### 3.2.4 Visit 2

The following procedures will be performed (any ocular measurement procedures outlined below will be carried out on each eye):

1. Medical and ocular history since the last visit will be recorded.

[REDACTED]

3. Slit lamp Biomicroscopy will be carried out for the signs outlined in Table 5 and in accordance with the current Eurolens Research Standard Operating Procedure 'Examination of the anterior segment using slit lamp Biomicroscopy'. Grades will be scored to the nearest 0.1 unit in the best judgement of the investigator using Efron Grading Scales. Corneal staining will be graded for five regions as described in [REDACTED]

Classification	Primary signs	Secondary signs
Signs	
[REDACTED]
 
Corneal staining Location of staining
 
[REDACTED]
	
[REDACTED]

Scale	Efron Grading Scales (scored to nearest 0.1) Corneal staining (see [REDACTED])	Efron Grading Scales (scored to nearest 0.1 except mucin balls, where the number is recorded)

Table 5: Biomicroscopic signs. Staining assessed with sodium fluorescein.

The presence of any ocular adverse events will be recorded, and reported as appropriate [REDACTED]

4. Subjects who have Type 2 or greater corneal staining and or corneal staining covering greater than 20% in any corneal region may be brought back for up to one repeat visit of this type, which may include some or all of the scheduled assessments.
5. Study lenses will be fitted according to the randomization table and allowed to settle for five minutes. Both investigator and subject are masked from the lenses and care system used, so the lenses will be provided in lens cases which do not detail lens or care system information. If a lens fails to settle within the first five minutes, e.g. excessive discomfort, or a suspicion that the lens is inverted, then the lens may be removed and a new lens reapplied.

[REDACTED]

[REDACTED]

[REDACTED]

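### Does the 0.80 power in section 1.5.1 need reworking because it names no comparison and swapping lens side with solution creates three kinds of pair?

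*Combined protocol and SAP*

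**What the plan says.** Section 1.5.1 (Power analysis) names corneal staining as the principal outcome. It takes 22 completers and a difference of 5 units on a 0-100 extent scale, and gives one power figure from one SD of within-subject differences: "assuming an alpha of 0.05, a two-tailed paired analysis and a standard deviation of intra-subject differences of 8 units) is 0.80". Recruitment is set at 28, which allows for losing 6/28 = 21.4%.

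Section 1.5 puts the hypothesis more broadly: "The principal hypothesis to be tested in this work is that biomicroscopy scores will not be different between the lens/solution combinations evaluated". Two lenses and two solutions make four combinations, hence six pairs. The analysis is to use linear regression or other parametric methods; parts of that section are redacted.

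Section 2.6.3 (Randomization of lenses and care regimens) has a different lens in each eye and one solution per day, and says that "the laterality of the lenses will be swapped for the second solution".

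**The concern.** The swap means that no two kinds of comparison share the same pairing:

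- Lens differs, solution the same (two pairs): opposite eyes, same day.
- Both differ (two pairs): same eye, different days.
- Solution differs, lens the same (two pairs): opposite eyes and different days.

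The third kind picks up both eye and day variation, so it looks like the noisiest. Section 1.1 motivates the study by "significant levels of corneal staining with certain combinations of contact lens types and care systems", which makes two solutions on the same lens a natural question. If the SD of 8 came from one of the other kinds of pair, a finding of no difference between solutions would carry less power than the 0.80 on which the target of 22 rests.

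**Working it through.** **Reproducing the plan's figure.** The inputs, all from section 1.5.1, are n = 22, difference 5, SD 8 and two-sided alpha 0.05. The noncentrality is (5/8) × √22 = 2.93 on 21 degrees of freedom, with critical value 2.08. The exact paired t-test gives power 0.798, which rounds to 0.80. With all 28 completing it is 0.890.

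**Simple model.** Write a score as subject + subject-by-day (variance d) + subject-by-eye (variance y) + residual (variance e). Each solution is worn on one day only, so d also holds any subject-by-solution variation. The variances of the paired differences are:

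- lens-only: 2(e + y)
- both differ: 2(e + d)
- solution-only: 2(e + d + y)

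Here solution-only is never smaller than the others. If 8 is the lens-only SD, then 2(e + y) = 64 and the solution-only SD is √(64 + 2d). The day SDs (√d) below are assumptions.

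| Day SD | Solution-only SD | Power, n = 22 | Power, n = 28 | Completers for 0.80 |
|---|---|---|---|---|
| 0 | 8.0 | 0.798 | 0.890 | 23 |
| 1 | 8.1 | 0.786 | 0.881 | 23 |
| 2 | 8.5 | 0.750 | 0.852 | 25 |
| 3 | 9.1 | 0.695 | 0.804 | 28 |
| 4 | 9.8 | 0.627 | 0.740 | 33 |

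**What the simple model leaves out.** It lets subjects differ in their response to the solution (inside d) but not in their response to the lens. Add a subject-by-lens variance l on the same footing:

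- lens-only: 2(e + y + l)
- both differ: 2(e + d + l)
- solution-only: 2(e + d + y)

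The three are now symmetrical: each carries two of the three components, and solution-only is the least precise only when l is below both d and y. With assumed components and n = 22:

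| e, d, y, l | Lens-only SD (power) | Both differ SD (power) | Solution-only SD (power) |
|---|---|---|---|
| 24, 16, 8, 0 | 8.00 (0.798) | 8.94 (0.706) | 9.80 (0.627) |
| 24, 4, 4, 4 | 8.00 (0.798) | 8.00 (0.798) | 8.00 (0.798) |
| 24, 4, 4, 8 | 8.49 (0.750) | 8.49 (0.750) | 8.00 (0.798) |
| 24, 8, 2, 6 | 8.00 (0.798) | 8.72 (0.728) | 8.25 (0.774) |

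For the third row, for example, lens-only is 2(24 + 4 + 8) = 72, SD 8.49, and solution-only is 2(24 + 4 + 4) = 64, SD 8.00. So solution-only can be the worst, the best or equal. One SD of 8 can fit all six pairs with d and y both above zero. Nor would 0.80 for solution-only pairs be a floor for the rest: in the third row the other two kinds have 0.750.

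**Averaged effects.** Averaging the solution difference over both lenses cancels eye and lens terms and leaves variance e + 2d. With e = 32 and y = 0, power at n = 22 is 0.977, 0.942, 0.885 and 0.798 for day SDs of 0, 2, 3 and 4.

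**Test level.** A paired test uses the SD of its own differences, so its level does not depend on the kind of pair. Simulation of the swapped layout under the simple model gave type I error between 4.6% and 5.3%.

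**The case for a change.** The strongest case for a change is that section 1.5.1 shows no redaction and still does not attach its 5 units and SD of 8 to any comparison, so the 0.80 cannot be matched to a hypothesis about four combinations. Modelling does not rescue a weak contrast: with complete data in this balanced layout, a mixed model has the same variance for the same-lens solution comparison as the paired difference. The protocol also rechecks staining before lens application at Visit 2, and section 3.2.4 provides that subjects with "corneal staining covering greater than 20% in any corneal region may be brought back for up to one repeat visit of this type", which suggests that days are not assumed identical. A clarifying sentence would be cheap.

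The first two points are right. The third is weaker: the recheck is an eligibility safeguard on pre-lens staining and does not measure how 2-hour scores vary between days. None of the three shows which kind of pair the SD of 8 describes, or that any pair falls short. The documents do not rank the same-lens solution comparison above the others either; section 1.3 asks about all combinations.

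**Conclusion.** No change to the plan follows. The power arithmetic is correct (0.798 against 0.80), and the missing label on the SD is a gap in description. From the documents one can say only that the three kinds of pair may have different SDs. Which is least precise depends on eye, day, subject-by-solution and subject-by-lens variances, none of which is given. The fall to 0.750, 0.695 or 0.627 rests on three assumptions together: that 8 is the lens-only SD, that subject-by-lens variance is nil, and that the day SD is 2, 3 or 4. At a day SD of 1 the loss is about one percentage point. On the same assumptions, if all 28 complete, power stays at 0.80 up to a day SD of about 3.

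An analyst facing this 2×2 within-subject layout would form per-subject contrasts, or fit the equivalent mixed model, and report each comparison with an interval based on its own variance. A finding of no difference would then be read from the precision achieved, which does not depend on the planning SD. The comparisons and model may also be set out in the redacted parts of section 1.5. Labelling the SD would tidy the text, but nothing in the documents shows that it would alter the sample size, the design or the validity of the tests.

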## Section 2. Resources

### 2.1 Subject selection

In this work 28 subjects will be enrolled, with an aim to complete 22 subjects.

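### Does the 0.80 power for one paired test at 0.05 fail to support a hypothesis about four lens/solution combinations?

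*Combined protocol and SAP*

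**What the plan says.** Section 1.5.1 names the outcome: "The principal outcome variable to be tested in this work is corneal staining". It then gives power 0.80 for a 5-unit difference in extent of staining on a 0-100 scale with 22 completers, "assuming an alpha of 0.05, a two-tailed paired analysis and a standard deviation of intra-subject differences of 8 units". Section 2.1 repeats the numbers: "28 subjects will be enrolled, with an aim to complete 22 subjects".

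Section 1.5 states the principal hypothesis as one of no difference: "biomicroscopy scores will not be different between the lens/solution combinations evaluated". On method it says that "these will be compared using linear regression models or other parametric methods". Parts of 1.5 are redacted, including text just before the sentence on deviations from the statistical plan. No redaction is visible in 1.5.1.

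The objective in 1.3 is to "compare the short-term clinical response to all combinations of two lens types" with two care systems. Under 2.6.3 each subject uses every combination over two dispensing visits, and the lenses change eyes for the second solution.

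**The concern.** Two lenses by two solutions make four combinations and 4 × 3 / 2 = 6 possible pairs. The power statement concerns a single paired difference and does not say which one. A reader may therefore take 0.80 at alpha 0.05 as applying to the whole four-combination hypothesis, which a single paired test cannot deliver. If every pair were tested, the trial would have either an overall error rate well above 0.05 or power well below 0.80 for each pair.

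The missing label also matters because the pairs differ in kind under 2.6.3:

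- Two lenses within one solution: same day, opposite eyes.
- Two solutions within one lens: different days, opposite eyes.
- The two pairs that differ in both lens and solution: same eye, different days.

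One SD of 8 need not fit all three kinds.

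**Working it through.** **Inputs.** From 1.5.1: n = 22 completers, difference 5, SD of within-subject differences 8, two-sided alpha 0.05. From 1.3 and 2.6.3: four combinations, all used by each subject. Assumed for every multi-condition figure below: SD 8 for every pair and no separate eye or day variance. Residual variance per condition is then 8² / 2 = 32.

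**The plan's own figure.** Paired t test, df = 21, noncentrality = 5 / (8/√22) = 2.93, critical value 2.080. Noncentral t power = 0.798, so the stated 0.80 is reproduced.

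**If all six pairs were tested.**

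- Each at 0.05, no true differences: 40,000 simulated trials of 22 subjects give a chance of about 0.21 of at least one false positive. For the four pairs that share a lens or a solution it is about 0.16.
- Bonferroni over six pairs (0.05/6 = 0.0083, critical value 2.912): power 0.52 per 5-unit pair.
- Bonferroni over four pairs (0.05/4 = 0.0125, critical value 2.732): power 0.59.
- Completers needed for 0.80 with Bonferroni: 35 for six pairs, 32 for four.

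**If one overall test is used.** F test on 3 and 63 df at 0.05, critical value 2.75, noncentrality = 22 × SS / 32, where SS is the sum of squared deviations of the four means from their average. The largest gap is 5 units in each row.

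| Pattern of means | SS | Noncentrality | Power |
|---|---|---|---|
| 0, 2.5, 2.5, 5 | 12.5 | 8.59 | 0.66 |
| 0, 0, 0, 5 | 18.75 | 12.89 | 0.84 |
| 0, 0, 5, 5 | 25 | 17.19 | 0.94 |

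**If a lens-by-solution model is used.** A main effect is the mean of two conditions minus the mean of the other two. Its within-subject variance is 32 × (1/2 + 1/2) = 32, so the SD is 5.66.

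- Main effect of 5: noncentrality = 5 / (5.66/√22) = 4.15. Power with 21 df is 0.977 at 0.05, 0.950 with Bonferroni over two main effects, and 0.928 over two main effects and the interaction.
- Only one combination differs by 5: each main effect is 2.5, noncentrality 2.07, power about 0.51 per main effect at 0.05. The overall test has 0.84 in that case.

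**What the figures show.** Power for the four-combination hypothesis runs from about 0.5 to about 0.98, depending on the analysis and the pattern of means. The low values come from all-pairs testing, or from patterns that dilute a main effect. None of them follows from the plan as written.

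**The case for a change.** The strongest case for a change is that the label costs only wording. Section 1.5.1 shows no redaction, so the unnamed pair is a real gap. An overall or factorial test is not the two-tailed paired analysis that 1.5.1 describes, and the overall test falls to 0.66 in one pattern. With only a family of methods visible, the choice of principal comparison appears open until the data are seen. Naming one comparison as principal and the rest as secondary would keep 0.80 and 22 completers intact.

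Part of this stands. A reader of 1.5.1 cannot tell which comparison has 0.80 power, and one SD may not suit every kind of pair.

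The rest does not carry. The redacted parts of 1.5 are where a contrast, model terms or a multiplicity rule would be expected, so the visible text cannot show that the choice is open. Making one pair confirmatory is also more than a label: it narrows the objective in 1.3, which is to compare all combinations. Statisticians could reasonably prefer an overall or factorial test that keeps that objective at the same sample size.

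Nor is there a conflict over the outcome. Sections 1.3 and 1.5 speak of biomicroscopy in general, and 1.5.1, a subsection of 1.5, narrows this to corneal staining.

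**Conclusion.** No change is called for. The 0.80 is correct for the single paired comparison that 1.5.1 describes, as a conventional basis for choosing 22 completers. Section 1.5 states one hypothesis, and an overall or lens-by-solution analysis tests it at 0.05 without six separate tests. The 0.21 error rate and the 0.52 power belong to an all-pairs analysis that the visible plan does not propose.

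The unstated pairing is a missing detail. Analysts can fill it sensibly when they specify the model, and the redacted text may already do so. This view rests on SD 8 for every pair, no eye or day variance, and the visible text alone. It would need revisiting if the redacted part of 1.5 made all six pairs principal with an adjustment, because the alpha of 0.05 in 1.5.1 would then not match that rule.
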